13.27 Study Monitoring

We will use an internal safety monitoring committee (SMC) comprised of experienced clinical researchers representing a diversity of backgrounds, skills and knowledge. The SMC helps investigators ensure subject safety, research integrity, and compliance with federal regulations and local policies. The SMC also makes recommendations to the PI that could include actions of continuation, modification, suspension, or termination.

The SMC will be able to meet on an adhoc basis to review any number of AE, SAE, or AE of special interest that may have met the stopping rules. They will determine if these events have met the criteria for halting the study. Recruiting will halt until the SMC has determine whether the stopping rules have been met. If the SMC determines the stopping rules have not been met then resumption of enrollment will continue.

Clinical site monitoring is conducted to ensure that the rights and well-being of human subjects are protected, that the reported trial data are accurate, complete, and verifiable, and that the conduct of the trial is in compliance with the currently approved protocol/amendment(s), with GCP, and with applicable regulatory requirements.

- Monitoring for this study will be performed by the University of Wisconsin Madison's Central Monitoring Service.
- On site monitoring will be conducted for this study which will include a site initiation visit, interim monitoring visits, and close out visit as outlined in the clinical monitoring plan.
 Monitoring will include review of regulatory files, investigational product, and up to 20% of subject records and data. Additional records may be reviewed, as needed, to ensure compliance with applicable regulatory requirements.

•	The sponsor-investigato visit.	r will be provided co	ppies of monitoring re	eports within 30 days of

14.0 RISK-BENEFIT

14.1 Risks of Study

The risks to subjects in this trial will be minimized by compliance with the eligibility criteria, clinical monitoring, adherence to protocol requirements, and investigator guidance regarding specific safety areas.

Appropriate medical treatment will be available to manage immediate allergic reactions in the event an acute anaphylactic reaction occurs following administration of the Novavax COVID-19 Vaccine, Adjuvanted.

Adverse reactions reported in clinical trials following administration of the Novavax COVID-19 Vaccine, Adjuvanted include injection site pain/tenderness, fatigue/malaise, muscle pain, headache, joint pain, nausea/vomiting, injection site redness, injection site swelling, fever, chills, injection site pruritus, hypersensitivity reactions, lymphadenopathy-related reactions, myocarditis, and pericarditis.

Myocarditis, pericarditis, anaphylaxis, paresthesia, and hypoesthesia have been reported following administration of the Novavax COVID-19 Vaccine, Adjuvanted outside of clinical trials.

The rate of IBD flares or solid organ transplant rejections will be evaluated in the study populations following the administration of the Novavax COVID-19 vaccine.

To ensure subject privacy, the study procedures will be performed in a private room. The study team members will be in a private space when conducting study phone/video calls with potential participants.

The specific safety areas that will be closely monitored in this subject population are the risk of flares post-immunization and the rates of transplant rejection.

Loss of confidentiality: There is a risk that the subject information could become known to someone not involved in this study.

Phlebotomy: Blood draws can cause bruising in the skin at the injection site and, rarely, infection in the skin. Rarely, dizziness or fainting occurs after blood is drawn.

14.2 Potential Benefits of Study

Beyond any protection from COVID-19 infection conferred by this vaccine booster dose, this study may benefit other people in the future by helping us learn more about immune responses to the recombinant COVID-19 vaccine in immunosuppressed populations, especially a mix and match strategy. This study will help determine whether patients with IBD on certain immunosuppressive regimens will require booster doses of COVID-19 vaccines.

15.0 STUDY FEASBILITY

Currently greater than 1500 patients are seen at UW health for the treatment of their inflammatory bowel disease and at least 800 transplants are performed annually. The majority of patients with IBD and solid organ transplant recipients who are seen at UW health facilities will be eligible to participate in our study. We have 6 providers that focus exclusively seen patients with IBD and the transplant surgery group consist of 13 faculty. We anticipate that we will be able to recruit 35 patients per month to participate in our study.

The primary outcome will be 1 month post-immunization, so we anticipate that we could submit this information as a late-breaking abstract to Digestive Disease Week 2025 in February 2025.

The study duration will be approximately 2 years. Each subject will be involved in the study for approximately 6 months.

The strengths of conducting studies at the University of Wisconsin include a collaborative team with research expertise, and access to the Wisconsin Immunization Registry (WIR), a state-wide computerized internet database that was developed to record and track immunization records of Wisconsin residents. The WIR captures 97% of vaccines administered in the state, 25 including data from both public and private providers, and 98.5% of Wisconsin residents have an active WIR record. We recently used the WIR to show high COVID-19 vaccine uptake among patients with IBD. 27

16.0 APPENDICES

16.1 Appendix 1: Short Crohn's Disease Activity Index (sCDAI)

The sCDAI uses the same scale as the full CDAI, such that scores <150 define remission, 150–219 mild activity, 220–450 moderate activity, and >450 severe activity. Computation is straightforward: ¹⁹

$$sCDAI{=}44{+}\left(2{*}{\sum\limits_{n=1}^{7}L}\right){+}\left(5{*}{\sum\limits_{n=1}^{7}A}\right){+}\left(7{*}{\sum\limits_{n=1}^{7}W}\right)$$

Where L is the number of liquid stools, A is the rating of abdominal pain (0–3, none to severe), W is the rating of general wellbeing (0–4, generally well to terrible), and n is the day of follow-up. In study 1, we estimated sCDAI scores from only 1 day of data by multiplying the individual component scores by 7.

16.2 Appendix 2: Simple Clinical Colitis Activity Index

Simple Clinical Colitis Activity Index (SCCAI)

Sub score Category	Scores				
	0	1	2	3	4
Bowel Frequency (day)	1-3	4-6	7-9	>9	
Bowel Frequency (night)	0	1-3	4-6		
Urgency of defecation	None	Hurry	Immediately	Incontinence	
Blood in stool	None	Trace	Occasionally frank	Usually frank	
General well-being	Very Well	Slightly below par	Poor	Very poor	Terrible
Extra-intestinal manifestations (arthritis, pyoderma gangrenosum, erythema nodosum, uveitis)		1 per manifestation			

A maximum score of 19 points:

- 1) Remission = Score of 0 to 4 points
- 2) Mild Activity = Score of 5 to 7 points
- 3) Moderate Activity = Score of 8 to 16 points
- 4) Severe Activity = Score of > 16 points

Appendix 2b: Pouchitis Disease Activity Index (PDAI)

Criteria		Score
Clinical	Stool frequency	
	Usual post-operative stool frequency	0
	1-2 stools/day > post-operative usual	1
	3 or more stools/day > post-operative usual	2
	Rectal bleeding	
	None or rare	0
	Present daily	1
	Fecal urgency or abdominal cramps	
	None	0
	Occasional	1
	Usual	2
	Fever (body temperature >37.8°C)	
	Absent	0
	Present	1
	• . •	

Score ≥6 pouchitis.

Score < 6 remission

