Success Criterion: Descriptive

6.4 Evaluate the disease activity following administration of the booster dose up to 30 days post-vaccination and during the whole post-vaccination follow-up period.

Disease activity will be assessed by monitoring disease activity using the Short Crohn's Activity Index (SCAI)¹⁹ for patients with Crohn's disease or the Simple Clinical Colitis Activity Index (SCCAI) questionnaire for patients with Ulcerative colitis at the baseline visit (V1), V2, and V3 visits. For patients with pouchitis we will use the simplified pouchitis disease activity index (PDAI). The incidence of IBD flares will be evaluated in all patients receiving recombinant boosters. This will be quantified by patients who were in clinical remission who develop a disease flare after receiving a recombinant COVID-19 booster.

Endpoint:

The number and percentage of participants reporting disease flares of IBD.

Success Criterion: Descriptive

6.5 Evaluate for solid organ transplant rejection following administration of booster dose, up to 30 days post-vaccination and during the whole post-vaccination follow-up period.

Participants will be asked if they have been diagnosed with acute rejection after their baseline visit (V1). Episodes of acute rejection will be collected by searching electronic medical records and asking patients at each clinic visit (V2 and V3). Acute rejection will be defined as a notation of a new episode of acute rejection (cellular or antibody-mediated), a steroid bolus and taper in the absence of another indication, or administration of a T or B cell depleting agent or immune globulin.²⁰

This will be quantified by patients who develop acute rejection of their transplant after receiving a recombinant COVID-19 booster.

Endpoint:

The number and percentage of participants reporting acute rejection of their transplant.

Success Criterion: Descriptive

[figure not shown]

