8.1 Inclusion criteria

- Patient is between the ages of 18-85 years.
- Patient has a history of ulcerative colitis (UC), Crohn's disease, pouchitis, or indeterminate colitis diagnosed by standard clinical, radiographic, endoscopic, and histopathologic criteria.

And/or patient is a solid organ transplant recipient (e.g. lung, kidney, liver)

- Have received at least three doses of a COVID-19 vaccine.
 - Three mRNA vaccines

Or

- One or two viral vector vaccine and one or two mRNA vaccines.
- Female participant of non-childbearing potential (pre-menarche, current tubal ligation, hysterectomy, oophorectomy or post-menopause) and childbearing potential (if they had: practiced adequate contraception (include -IUD or equivalent, hormonal contraceptive (e.g. pill, patch, ring, implant or an injection used consistently and that has reached full effect prior to the first dose of vaccine), hysterectomy and/or a bilateral tubal ligation or bilateral oophorectomy) for 1 month prior to vaccination and agreement to use such for an additional 8 weeks after administration of the Novavax COVID-19 vaccine). Non-pregnant females with a negative pregnancy test who are willing to practice adequate contraception 8 weeks after administration of the Novavax COVID-19 vaccine.
- On one of the following treatment regimens
 - o IBD
 - Thiopurine Therapy Group: on azathioprine at least 2.0mg/kg or 6MP 1.0mg/kg
 - Anti-TNF Therapy Group: on maintenance therapy infliximab (at least every 8 weeks), golimumab (at least monthly), adalimumab (at least every 2 weeks), or certolizumab (at least monthly)
 - Anti-TNF Combination Therapy Group: on anti-TNF therapy as described above along with either 15mg of methotrexate or azathioprine at least 1.0mg/kg or 6MP 0.5mg/kg.
 - Vedolizumab Therapy Group: either vedolizumab monotherapy at least every 8 week dosing or combination therapy Group: on vedolizumab therapy at with azathioprine or methotrexate
 - Ustekinumab Therapy Group: either ustekinumab monotherapy or combination therapy with methotrexate or azathioprine.
 - Tofacitinib Therapy Group: on tofacitinib at least 5mg PO twice daily
 - Risankizumab Therapy: 360mg at least every 8 weeks
 - Mirikizumab: 200mg at least every 4 weeks
 - Upadacitinib Therapy Group: on upadacitinib at least 15mg PO daily
 - Ozanimod: at least 0.92mg once daily
 - Etrasimod: at least 2mg once daily

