8.2 Exclusion criteria

A patient will not be eligible for inclusion in this study if they meet any of the following criteria.

- Allergy to recombinant COVID-19 vaccine or any component of it
- Patient cannot or will not provide written informed consent.
- Unable to provide appropriate informed consent because of illiteracy or impairment in decision-making capacity.
- Active antibody-mediated or cellular rejection within the past six months
- Recent IBD flare requiring initiation of systemic corticosteroids within the past month
- Previous history of myocarditis or pericarditis ever.
- Patients who are pregnant
- Patients who are lactating
- Patients with an active COVID-19 infection
- Patients with a COVID-19 infection within the past two months

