13.21 Adverse Events of Special Interest

Myocarditis and pericarditis will be adverse events of special interest. All patients will be counseled on the potential risk of myocarditis or pericarditis from COVID-19 vaccination.

- 1) Potential myocarditis and pericarditis events
- a. Participants reporting acute chest pain, shortness of breath, palpitations, or other signs or symptoms of myocarditis or pericarditis within 4 to 6 weeks after vaccination must be referred to a cardiologist for evaluation and management.
- b. Cases of myocarditis and pericarditis will be followed until resolution of symptoms and abnormal test findings.

Myocarditis and pericarditis cases will be defined by based on the Centers for Disease Control and Prevention (CDC) care definition. ²³ (Appendix 5)

- 2) IBD flares will be evaluated based on SCAI, PDAI, and SCCAI based on follow-up at V1, V2, & V3..
- 3) Solid organ transplant rejection will be reviewed based on follow-up at V1, V2, & V3. Episodes of acute rejection will be documented by chart review.

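### Appendix 2b sets the pouchitis cut-off at the highest score the trial can record, so every lower score is labelled remission

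*Combined protocol and SAP*

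**What the plan says.** Section 6.4 assigns a disease activity index by diagnosis and measures it at V1, V2 and V3: "For patients with pouchitis we will use the simplified pouchitis disease activity index (PDAI"). The flare measure depends on remission: "This will be quantified by patients who were in clinical remission who develop a disease flare after receiving a recombinant COVID-19 booster". The endpoint is "The number and percentage of participants reporting disease flares of IBD", with a descriptive success criterion. Section 13.21 repeats the dependence on the indices: "IBD flares will be evaluated based on SCAI, PDAI, and SCCAI based on follow-up at V1, V2, & V3".

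Appendix 2b prints four items, all under a clinical heading: stool frequency (0 to 2), rectal bleeding (0 to 1), urgency or cramps (0 to 2) and fever (0 to 1). Below them stand two labels, "Score ≥6 pouchitis" and "Score < 6 remission". No other pouchitis threshold appears in the documents.

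The index is collected by questioning participants about symptoms (section 10.4.2). Neither the calendar in section 10.1 nor the visit lists in section 10.2 include endoscopy or histology.

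**The concern.** A threshold for active disease should lie inside the range of the scale, so that clearly symptomatic people fall above it. Here it lies at the very top. A participant with marked symptoms on three of the four items is still called in remission if the fourth is not also at its maximum.

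Entry criteria do not keep such participants out at V1. Eligibility asks for a history of disease, including "pouchitis, or indeterminate colitis diagnosed by standard clinical, radiographic, endoscopic, and histopathologic criteria", and the only exclusion for current IBD activity in section 8.2 is "Recent IBD flare requiring initiation of systemic corticosteroids within the past month". Someone with symptomatic pouchitis and no recent new steroid course can therefore be enrolled.

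At stake is the meaning of a named secondary safety endpoint in these participants. If the labels are used, the group at risk of a flare can include people with active disease, and the flare count responds only to a move into the single top score.

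**Working it through.** The plan states no maximum score and no derivation of the cut-off, so there is no planned figure to reproduce. The check is an exact count from Appendix 2b.

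**Inputs (Appendix 2b).** Stool frequency has 3 levels (maximum 2), bleeding 2 levels (maximum 1), urgency or cramps 3 levels (maximum 2), and fever 2 levels (maximum 1). Cut-off: 6.

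**Maximum score.** 2 + 1 + 2 + 1 = 6, equal to the cut-off.

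**Item patterns.** 3 × 2 × 3 × 2 = 36, distributed as follows:

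| Total score | 0 | 1 | 2 | 3 | 4 | 5 | 6 |
|---|---|---|---|---|---|---|---|
| Patterns | 1 | 4 | 8 | 10 | 8 | 4 | 1 |

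One pattern, with all four items at maximum, reaches 6. The other 36 − 1 = 35 are labelled remission. These are possible patterns, not patient frequencies.

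**Worked cases.** Without fever the highest score is 2 + 1 + 2 + 0 = 5. Without daily bleeding it is 2 + 0 + 2 + 1 = 5. Either participant is in remission under the printed rule, whatever the other items show.

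**Changes over time, if a flare means moving from below 6 to 6.** A rise from 0 to 5 (5 points) is not counted. A rise from 5 to 6 (1 point) is counted.

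**Comparison within the protocol.** The SCCAI in Appendix 2 has a maximum of 3 + 2 + 3 + 3 + 4 + 4 = 19, with remission at 0 to 4 and graded bands above. Remission on the pouchitis index runs to 5 out of 6.

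**Can the size of the error be derived?** Suppose the right cut-off were some lower value c. Counting V1-to-V2 score pairs on the 0 to 6 scale:

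- Flares under c: V1 below c and V2 at c or above, c × (7 − c) pairs.
- Of these, missed by the printed rule: V2 from c to 5, c × (6 − c) pairs.
- Counted by the printed rule but not under c: V1 from c to 5 and V2 = 6, 6 − c pairs.

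At c = 1 the rule misses 1 × 5 = 5 of 1 × 6 = 6 pairs and adds 6 − 1 = 5. At c = 5 it misses 5 × 1 = 5 of 5 × 2 = 10 and adds 6 − 5 = 1. The missed share thus runs from one half to five sixths depending on a cut-off the documents do not give. The pairs are also unweighted, because no score distribution is given. No patient-level size or net direction follows.

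**The case against.** **The link to the endpoint is inferred.** Appendix 2b labels 6 or more as pouchitis, not as a flare, and no section says that a pouchitis flare means crossing 6. The endpoint wording could also be read as self-reported flares. This stands as a limit on the claim. Against it, section 6.4 makes remission the starting state, section 13.21 evaluates flares from the indices, and Appendix 2b holds the only pouchitis threshold.

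**Text may be missing from the table.** A stray mark follows the fever row in the extracted appendix. Lost endoscopy or histology rows would not help, since neither is scheduled. A lost scoring note could change the conclusion.

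**The reach is small.** The synopsis gives 21 enrolled and no further recruitment. Pouchitis is one of several eligible diagnoses, and the number enrolled may be zero. The endpoint is descriptive. Deterioration of a baseline condition is recorded as an AE (section 13.23), and medically attended AEs are collected for six months (section 13.1). Clinically important worsening would probably be recorded somewhere, though not necessarily in the flare count. All of this stands.

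**Stronger readings.** A reader might infer that most pouchitis flares will be missed and that the reported rate is too low. The documents do not support that: the missed share depends on an unstated alternative cut-off, and the rule can also add flares by treating a V1 score of 5 as remission. A reader might also infer that the stopping rule in section 13.26 is compromised, because it needs a moderate band that Appendix 2b lacks. The band is missing, but with recruitment closed the rule has little left to act on.

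**Conclusion.** The concern holds on the printed text: the cut-off equals the maximum of what the trial collects, and a participant is classed as in remission unless all four items are at their maximum. That part is exact arithmetic and needs no outside source.

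The consequence for the section 6.4 flare count is conditional. It assumes that the Appendix 2b labels define remission and flare for pouchitis, and that no scoring note was lost from the table. On those assumptions the count in pouchitis participants is not interpretable, but by how much and in which net direction cannot be stated. Severity is minor. Confidence is medium, because of the inferred link and the possible lost text.

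**What to change.** Change Appendix 2b, section 6.4 and the SAP that section 12.2 says will be written ahead of database lock. Suggested wording:

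*The labels at 6 or more and below 6 are not applied to the 0 to 6 clinical score. For each pouchitis participant, item scores and total score at V1, V2 and V3, and the change from V1, are listed beside any gastrointestinal or pouch-related adverse event. Pouchitis participants are reported separately from the index-based remission-to-flare count.*

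If no pouchitis participant was enrolled, one sentence in the report saying so is enough.

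A replacement binary cut-off is not recommended. The documents give no basis for one, and it would be set after enrolment in an unblinded study.

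The cost is a few sentences and one small listing, for at most 21 participants, of item data already scheduled. No new visits or samples are needed. The price is that no binary index-based flare rate is available for pouchitis.

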16.3 Appendix 3: List of potential Immune-mediated Diseases (pIMDs)

Medical Concept	Additional Notes
Blood disorders and coagulor	pathies
Antiphospholipid syndrome	
Autoimmune aplastic	
anemia	
Autoimmune hemolytic	Includes warm antibody hemolytic anemia and cold antibody
anemia	hemolytic anemia
Autoimmune	
lymphoproliferative	
syndrome (ALPS)	
Autoimmune neutropenia	
Autoimmune pancytopenia	
Autoimmune	Frequently used related terms include: "autoimmune
thrombocytopenia	thrombocytopenic purpura", "idiopathic thrombocytopenic
	purpura (ITP)", "idiopathic immune thrombocytopenia",
 	"primary immune thrombocytopenia".
Evans syndrome	
Pernicious anemia	
Thrombosis with	
thrombocytopenia	
syndrome (TTS)	

Medical Concept	Additional Notes		
Thrombotic	Also known as "Moschcowitz-syndrome" or		
thrombocytopenic purpura	"microangiopathic hemolytic anemia"		
Cardio-pulmonary inflammato			
Idiopathic	Including but not limited to:		
Myocarditis/Pericarditis	Autoimmune / Immune-mediated myocarditis		
	Autoimmune / Immune-mediated pericarditis		
	Giant cell myocarditis		
Idiopathic pulmonary	Including but not limited to:		
fibrosis	Idiopathic interstitial pneumonia (frequently used related)		
	terms include "Interstitial lung disease", "Pulmonary fibrosis",		
	"Immune-mediated pneumonitis")		
	 Pleuroparenchymal fibroelastosis (PPFE) 		
Pulmonary alveolar	Frequently used related terms include: "pulmonary alveolar"		
proteinosis (PAP)	lipoproteinosis", "phospholipidosis"		
Endocrine disorders			
Addison's disease			
Autoimmune / Immune-	Including but not limited to:		
mediated thyroiditis	• Hashimoto thyroiditis (autoimmune hypothyroidism,		
	lymphocytic thyroiditis)		
	Atrophic thyroiditis		
	Silent thyroiditis		
	Thyrotoxicosis		
Autoimmune diseases of the	Includes autoimmune oophoritis, autoimmune ovarian		
testis and ovary	failure and autoimmune orchitis		
Autoimmune hyperlipidemia			
Autoimmune hypophysitis Diabetes mellitus type I			
Grave's or Basedow's	Includes Marine Lenhart syndrome and Graves'		
disease	ophthalmopathy, also known as thyroid eye disease (TED)		
discuss	or endocrine ophthalmopathy		
Insulin autoimmune	or original optimismispanty		
syndrome			
Polyglandular autoimmune	Includes Polyglandular autoimmune syndrome type I, II and		
syndrome	III		
Eye disorders			
Ocular Autoimmune /	Including but not limited to:		
Immune-mediated disorders	Acute macular neuroretinopathy (also known as acute		
	macular outer retinopathy)		
	Autoimmune / Immune-mediated retinopathy		
	Autoimmune / Immune-mediated uveitis, including idiopathic		
	uveitis and sympathetic ophthalmia		
	Cogan's syndrome: an oculo-audiovestibular disease		
	Ocular pemphigoid		
	Ulcerative keratitis		
	Vogt-Koyanagi-Harada disease		
Gastrointestinal disorders			
Autoimmune / Immune-			
mediated pancreatitis			

Medical Concept	Additional Notes	
Celiac disease		
Hepatobiliary disorders		
Autoimmune cholangitis		
Autoimmune hepatitis		
Primary biliary cirrhosis		
Primary sclerosing		
cholangitis		
Musculoskeletal and connect	ve tissue disorders	
Gout	Includes gouty arthritis	
Idiopathic inflammatory	Including but not limited to:	
myopathies	Dermatomyositis	
	Inclusion body myositis	
	Immune-mediated necrotizing myopathy	
	Polymyositis	
Mixed connective tissue		
disorder		
Polymyalgia rheumatica (PMR)		
Psoriatic arthritis (PsA)		
Relapsing polychondritis		
Rheumatoid arthritis	Including but not limited to:	
	Rheumatoid arthritis associated conditions	
	Juvenile idiopathic arthritis	
	Palindromic rheumatism	
	Still's disease	
	Felty's syndrome	
Sjögren's syndrome		
Spondyloarthritis	Including but not limited to:	
' '	Ankylosing spondylitis	
	Juvenile spondyloarthritis	
	Keratoderma blenorrhagica	
	Psoriatic spondylitis	
	Reactive Arthritis (Reiter's Syndrome)	
	Undifferentiated spondyloarthritis	
Systemic Lupus	Includes Lupus associated conditions (e.g. Cutaneous lupus)	
Erythematosus	erythematosus, Lupus nephritis, etc.) or complications such	
,	as shrinking lung syndrome (SLS)	
Systemic Scleroderma	 Includes Reynolds syndrome (RS), systemic sclerosis with 	
(Systemic Sclerosis)	diffuse scleroderma and systemic sclerosis with limited	
	scleroderma (also known as CREST syndrome)	
Neuroinflammatory/neuromuscular disorders		
Acute disseminated	Includes the following:	
encephalomyelitis (ADEM)	Acute necrotising myelitis	
and other inflammatory-	Bickerstaff's brainstem encephalitis	
demyelinating variants	Disseminated necrotizing leukoencephalopathy (also known)	
, ,	as Weston-Hurst syndrome, acute hemorrhagic leuko-	
	encephalitis, or acute necrotizing hemorrhagic	
	encephalomyelitis)	
	/	

Medical Concept	Additional Notes
Wedical Collecti	Myelin oligodendrocyte glycoprotein antibody-associated
	disease
	Neuromyelitis optica (also known as Devic's disease)
	Noninfective encephalitis / encephalomyelitis / myelitis
	Postimmunization encephalomyelitis
Guillain-Barré syndrome	Includes variants such as Miller Fisher syndrome and the
(GBS)	acute motor and sensory axonal neuropathy (AMSAN)
Idiopathic cranial nerve	Including but not limited to:
palsies/paresis and	Cranial nerve neuritis (e.g. Optic neuritis)
inflammations (neuritis)	Idiopathic nerve palsies/paresis (e.g. Bell's palsy)
	Melkersson-Rosenthal syndrome
	Multiple cranial nerve palsies/paresis
Multiple Sclerosis (MS)	Includes the following:
	Clinically isolated syndrome (CIS)
	NA 12 (NAO (U NA 1 () () () ()
	· · · · · · · · · · · · · · · · · · ·
	Primary-progressive MS (PPMS) Padialagianly isolated syndroms (DIS)
	Radiologically isolated syndrome (RIS) Replication (RIS)
	Relapsing-remitting MS (RRMS)
	Secondary-progressive MS (SPMS)
	Uhthoff's phenomenon
Myasthenia gravis	Includes ocular myasthenia and Lambert-Eaton myasthenic
	syndrome
Narcolepsy	• Includes narcolepsy with or without presence of
	unambiguous cataplexy
Peripheral inflammatory	Including but not limited to:
demyelinating neuropathies	Acute Brachial Radiculitis (also known as Parsonage-Turner)
and plexopathies	Syndrome or neuralgic amyotrophy)
	Antibody-mediated demyelinating neuropathy
	Chronic idiopathic axonal polyneuropathy (CIAP)
	Chronic Inflammatory Demyelinating
	Polyradiculoneuropathy (CIDP), including atypical CIDP
	variants (e.g. multifocal acquired demyelinating sensory and
	motor neuropathy also known as Lewis-Sumner syndrome)
	Multifocal motor neuropathy (MMN)
Transverse myelitis (TM)	
Transverse myenus (Tivi)	Includes acute partial transverse myelitis (APTM) and acute acmplete transverse myelitis (ACTM)
Renal disorders	complete transverse myelitis (ACTM)
Autoimmune / Immune-	Including but not limited to:
mediated glomerulonephritis	
mediated giomerdionepillitis	
	IgM nephropathy
	C1q nephropathy
	Fibrillary glomerulonephritis
	Glomerulonephritis rapidly progressive
	Membranoproliferative glomerulonephritis
	Membranous glomerulonephritis
	Mesangioproliferative glomerulonephritis
	Tubulointerstitial nephritis and uveitis syndrome

Medical Concept	Additional Notes
	P. I
Skin and subcutaneous tissue	e disorders
Alopecia areata	La alta alle an hand an ad Peredia al da a
Autoimmune / Immune-	Including but not limited to:
mediated blistering	Bullous Dermatitis
dermatoses	Bullous Pemphigoid
	Dermatitis herpetiformis
	Epidermolysis bullosa acquisita (EBA)
	• Linear IgA-mediated bullous dermatosis (LABD), also known
	as Linear IgA disease
En theme multiforms	Pemphigus
Erythema multiforme Erythema nodosum	
Reactive granulomatous	Including but not limited to
dermatitis	Interstitial granulomatous dermatitis
dermanus	 Palisaded neutrophilic granulomatous dermatitis
Lichen planus	Includes liquen planopilaris
Localised Scleroderma	Includes Eosinophilic fasciitis (also called Shulman
(Morphoea)	syndrome)
Psoriasis	
Pyoderma gangrenosum	
Stevens-Johnson Syndrome	Including but not limited to:
(SJS)	 Toxic Epidermal Necrolysis (TEN)
	SJS-TEN overlap
Sweet's syndrome	Includes Acute febrile neutrophilic dermatosis
Vitiligo	
Vasculitis	
Large vessels vasculitis	Including but not limited to:
	Arteritic anterior ischemic optic neuropathy (AAION or
	arteritic AION)
	Giant cell arteritis (also called temporal arteritis)
NA diama at 1 1/	Takayasu's arteritis
Medium sized and/or small	Including but not limited to:
vessels vasculitis	Anti-neutrophil cytoplasmic antibody (ANCA) positive
	vasculitis (type unspecified)
	Behcet's syndrome Buorger's disease (thromboongiitis obliterane)
	Buerger's disease (thromboangiitis obliterans) Churg Strauge avadreme (allergie grapulemeteus angiitis)
	Churg–Strauss syndrome (allergic granulomatous angiitis) Trythoma induratum (alea known as nodular vasquiitis)
	Erythema induratum (also known as nodular vasculitis)Henoch-Schonlein purpura (also known as IgA vasculitis)
	 Henoch-Schonlein purpura (also known as IgA vasculitis) Microscopic polyangiitis
	Necrotizing vasculitis
	Polyarteritis nodosa
	 Single organ cutaneous vasculitis, including leukocytoclastic
	vasculitis, hypersensitivity vasculitis and acute hemorrhagic
	edema of infancy (AHEI)
	Wegener's granulomatosis
	5 5

Medical Concept	Additional Notes	
Other (including multisystemic)		
Anti-synthetase syndrome		
Capillary leak syndrome	 Frequently used related terms include: "systemic capillary leak syndrome (SCLS)" or "Clarkson's Syndrome" 	
Goodpasture syndrome	 Frequently used related terms include: "pulmonary renal syndrome" and "anti-Glomerular Basement Membrane disease (anti-GBM disease)" 	
Immune-mediated enhancement of disease	 Includes vaccine associated enhanced disease (VAED and VAERD). Frequently used related terms include "vaccine- mediated enhanced disease (VMED)", "enhanced respiratory disease (ERD)", "vaccine-induced enhancement of infection", "disease enhancement", "immune enhancement", and "antibody-dependent enhancement (ADE) 	
Immunoglobulin G4 related disease		
Langerhans' cell histiocytosis		
Multisystem inflammatory	Including but not limited to:	
syndromes	Kawasaki's disease	
	 Multisystem inflammatory syndrome in adults (MIS-A) 	
	 Multisystem inflammatory syndrome in children (MIS-C) 	
Overlap syndrome		
Raynaud's phenomenon		
Sarcoidosis	Includes Loefgren syndrome	
Susac's syndrome		

Appendix 4. Centers for Disease Control and Prevention: Case definitions of probable and confirmed myocarditis, pericarditis, and myopericarditis

Condition	Definition
Acute myocarditis	PROBABLE
-	Presence of ≥1 new or worsening of the following clinical symptoms:*
	chest pain, pressure, or discomfort
	dyspnea, shortness of breath, or pain with breathing
	• palpitations
	• syncope
	OR, infants and children aged
	<12 years might instead have ≥2 of the following symptoms:
	irritability
	• vomiting
	poor feeding • tachypnea
	• lethargy
	AND
	≥1 new finding of

	_
	 troponin level above upper limit of normal (any type of troponin) abnormal electrocardiogram (ECG or EKG) or rhythm monitoring findings consistent with myocarditis§ abnormal cardiac function or wall motion abnormalities on echocardiogram cMRI findings consistent with myocarditis¶ AND No other identifiable cause of the symptoms and findings CONFIRMED Presence of ≥1 new or worsening of the following clinical symptoms:* chest pain, pressure, or discomfort dyspnea, shortness of breath, or pain with breathing
	 palpitations syncope OR, infants and children aged <12 years might instead have ≥2 of the following symptoms: irritability vomiting poor feeding • tachypnea lethargy
	AND ≥1 new finding of • Histopathologic confirmation of myocarditis† • cMRI findings consistent with myocarditis¶ in the presence of troponin level above upper limit of normal (any type of troponin) AND • No other identifiable cause of
Acute pericarditis**	the symptoms and findings Presence of ≥2 new or worsening of the following clinical features: • acute chest pain†† • pericardial rub on exam • new ST-elevation or PR-depression on EKG • new or worsening pericardial effusion on echocardiogram or MRI
Myopericarditis	This term may be used for patients who meet criteria for both myocarditis and pericarditis.

Abbreviations: AV = atrioventricular; cMRI = cardiac magnetic resonance imaging; ECG or EKG = electrocardiogram.

^{*} Persons who lack the listed symptoms but who meet other criteria may be classified as subclinical myocarditis (probable or confirmed).

[†] UsingtheDallascriteria(AretzHT,BillinghamME,EdwardsWD,etal.Myocarditis. A histopathologic definition and classification. Am J Cardiovasc Pathol 1987; 1:3–14). Autopsy cases may be classified as confirmed clinical myocarditis on the basis of meeting histopathologic criteria if no other identifiable cause.

§ To meet the ECG or rhythm monitoring criterion, a probable case must include at least one of 1) ST-segment or T-wave abnormalities; 2) Paroxysmal or sustained atrial, supraventricular, or ventricular arrhythmias; or 3) AV nodal

¶ conduction delays or intraventricular conduction defects.

Using either the original or the revised Lake Louise criteria. https://www.sciencedirect.com/science/article/pii/S0735109718388430?via%3Dihub

** https://academic.oup.com/eurheartj/article/36/42/2921/2293375

†† Typically described as pain made worse by lying down, deep inspiration, or cough, and relieved by sitting up or leaning forward, although other types of chest pain might occur.

